17. STATISTICAL METHODS AND DETERMINATION OF SAMPLE SIZE

A prospective, randomized (1:1:1), double-blind, multi-center, placebo-controlled clinical study.

Statistical Hypothesis

The hypothesis of this study is that treating with CimetrA and CimetrA2 will be more effective, while maintaining a favorable safety profile. This will be demonstrated by a significant difference between the two active and the control groups.

	MGC Pharma Clinical Study Protocol	Protocol No.: MGC-009
		Version 02, 05 Sep 2021
		Page 60 of 76
A Phase IIb, double blind, placebo-controlled clinical study designed to evaluate the effect of Cimetra in patients diagnosed with COVID-19		CONFIDENTIAL

In this study, we will test the following hypothesis:

- H0: $\Delta_1 = \Delta_2 = \Delta_3$
- H1: at least one is different.

Where Delta is the difference between baseline and end of study in WHO Ordinal Scale for clinical trial.

If the null hypothesis is rejected in favor of the alternative hypothesis the study will be deemed successful.

Safety will be assessed by adverse events, blood and urine laboratory assessments and vital signs.

Planned Sample Size

For this phase IIb, 3-armed clinical trial, we use the ANOVA test to estimate the expected improvement in the primary outcome; the WHO ordinal scale for clinical improvement.

We expect medium effect ($f=0.20$) for the differences in Delta between the 3 groups, and standard deviation of 1.5, based on the ordinal scale (0-8). This power analysis is for a one-way fixed effects analysis of variance with 3 levels. The study will include 80 patients per group for a total of 240 patients.

The criterion for significance (α) has been set at 0.05 with Power of at least 80%.

The analysis of variance is two-tailed Main effects.

For immunogenicity assessment, larger sample size will reduce mean variability in the observed outcomes and will increase the opportunity to detect real changes.

For 80 participants per group we ensure the desired precision for phase 3 trial to assess safety and effectiveness. Total sample 240 patients.

Computer Software

	MGC Pharma Clinical Study Protocol	Protocol No.: MGC-009
		Version 02, 05 Sep 2021
		Page 61 of 76
A Phase IIb, double blind, placebo-controlled clinical study designed to evaluate the effect of CimetrA in patients diagnosed with COVID-19		CONFIDENTIAL

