The overall significance level for this study is 5% using two-tailed tests, except for treatment by center/region interaction that will be tested at a significance level of 10%.

When multiple comparisons between the groups are made, the chance of finding a significant difference in one of the comparisons is greater than the stated significance level, therefore we will use pot-hoc analysis.

Efficacy endpoints:

Time to sustained clinical improvement (as defined earlier).

Safety Endpoints

The safety endpoints of adverse events and tolerability will be assessed by review of all safety parameters, including adverse events.

	MGC Pharma Clinical Study Protocol	Protocol No.: MGC-009
		Version 02, 05 Sep 2021
		Page 63 of 76
A Phase IIb, double blind, placebo-controlled clinical study designed to evaluate the effect of CimetrA in patients diagnosed with COVID-19		CONFIDENTIAL

The incidence of adverse events will be assessed as a function of severity and association to the device. The time of resolution of the adverse events and need for treatment will also be analyzed.

Analysis Sets

The ITT analysis set will serve as the main set for safety assessments.

The primary and secondary performance efficacy assessments will also be performed on the PP and the ITT analysis sets.

Statistical Analysis

Demographic and Baseline

Demographic and baseline condition related characteristics will be tabulated and compared between the study arms by data type. Continuous variables will be summarized by a mean, standard deviation, minimum, median and maximum and categorical variables by a count and percentage.

Primary Efficacy Analysis

The primary efficacy endpoint of the study is the mean change in the WHO Ordinal Scale. It will be evaluated using a General Linear Model ANOVA test.

Subset Analyses

The primary endpoint will also be evaluated stratified by center using a General Linear Model ANOVA test.

A sensitivity analysis of the primary endpoint will be performed to assess the impact of missing data on the study outcome.

Adjustment for other covariates such as demographics or other baseline participant characteristics may be performed by adding these variables into a multivariate linear regression.

Secondary Efficacy Analysis

	MGC Pharma Clinical Study Protocol	Protocol No.: MGC-009
		Version 02, 05 Sep 2021
		Page 64 of 76

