A Phase IIb, double blind, placebo-controlled clinical study designed to evaluate the effect of CimetrA in patients diagnosed with COVID-19		CONFIDENTIAL

The 3 groups will be compared with the ANOVA test or Kruskal Wallis non-parametric test, following by post-hoc analysis for pairs differences.

Additional Efficacy Parameters of Interest

A count and percentage of participants responding to each of the exploratory efficacy endpoints will be presented. The groups will be compared with a chi-squared test or a Fisher’s exact test.

Safety Analysis

The primary safety variable, the cumulative incidence (and 95% CI) of device related adverse events (AEs) throughout the study, will be presented in tabular format and will include incidence tables by severity.

Serious adverse events, device-related SAEs, adverse events (by type and overall), device-related AE, adverse device reactions and device malfunction rates will be compared between the study arms with a Fisher’s exact test.

Serious adverse events will be listed and discussed individually.

PK test

Actual times of dosing and blood collection at various time points will be recorded in source documents as well as CRF’s. Objectives of PK sampling are to measure values of CimetrA active ingredients in plasma at different time point after first administration of study medications and at different time point after multiple administrations during steady state.

PK samples will be processed and frozen on site. Labels have been prepared for the site again containing patient No., visit No., type of test (PK) and time point. Upon completion of the study, samples will be sent to selected analytical laboratory with dedicated courier service. The PK parameters will be obtained from plasma concentration data for curcumin and boswellia.

	MGC Pharma Clinical Study Protocol	Protocol No.: MGC-009
		Version 02, 05 Sep 2021
		Page 65 of 76
A Phase IIb, double blind, placebo-controlled clinical study designed to evaluate the effect of Cimetra in patients diagnosed with COVID-19		CONFIDENTIAL

Analyses of PK data will be based on the PK Set, which will include all subjects who received at least one treatment and for whom concentration data is available.

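### The primary ANOVA of mean change treats the 0-8 WHO ordinal scale as equally spaced; the estimate depends on the label spacing, and power against a general shift is usually below that of an ordinal analysis, by an amount the protocol does not determine

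*Protocol*

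**What the plan says.** Protocol section 9.1 lists the WHO scale as nine ordered states: 0 is uninfected, 1 and 2 ambulatory, 3 and 4 hospitalized with moderate disease, 5 to 7 hospitalized with severe disease, and 8 dead. Sections 11.1 and 11.2 require hospitalization and exclude scores of 5 or more, so baseline can only be 3 or 4.

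Section 17 defines the quantity tested: "Where Delta is the difference between baseline and end of study in WHO Ordinal Scale for clinical trial". Under Primary Efficacy Analysis it states "The primary efficacy endpoint of the study is the mean change in the WHO Ordinal Scale" and "It will be evaluated using a General Linear Model ANOVA test". The null hypothesis is equality of the three Deltas, and rejecting it makes the study a success. The sample size uses the same method: "we use the ANOVA test to estimate the expected improvement in the primary outcome; the WHO ordinal scale for clinical improvement". Its inputs are f = 0.20 "for the differences in Delta between the 3 groups, and standard deviation of 1.5", with 80 patients per group.

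A rank test appears only under Secondary Efficacy Analysis: "The 3 groups will be compared with the ANOVA test or Kruskal Wallis non-parametric test". No rank or ordinal method is named for the primary endpoint. Its one named sensitivity analysis concerns missing data.

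**The concern.** The one-point steps do not mean the same thing. Moving from independent to assisted while ambulatory counts one point, and so does moving from ventilation with organ support to death. A difference in mean change adds such steps together, so its size depends on how the states happen to be numbered.

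Patients enter at 3 or 4. If most have left hospital by day 28 and a few have deteriorated or died, the scores are skewed to the right. A mean-based test can then be inefficient against a broad shift toward better states. Subtracting a baseline that takes only two adjacent values adds noise if it predicts the outcome poorly. Because the protocol itself fixes this test as the success criterion, the matter is not one left open for a statistical analysis plan.

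**Working it through.** **1. The plan's own figure.** Inputs from section 17: f = 0.20, three groups, N = 240, and significance and power "has been set at 0.05 with Power of at least 80" percent. The noncentrality is f²N = 0.04 × 240 = 9.6 with 2 and 237 degrees of freedom, which gives 79.3% power. Reaching 80% takes 82 per group (246). The figure reproduces to within rounding, with no margin. At SD 1.5 the SD of the group means is 0.20 × 1.5 = 0.30 points. If both doses work equally, that is a difference from placebo of 0.30 × 3/√2 = 0.64 points.

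**2. What the SD must cover.** The plan gives "standard deviation of 1.5, based on the ordinal scale (0-8") without saying whether deaths scored 8 are included. Suppose it describes survivors only, with survivor mean μ and an equal death fraction p in every arm:

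- variance = (1 − p) × 2.25 + p(1 − p)(8 − μ)²
- f = 0.30(1 − p) / SD

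| Deaths | SD (μ = 2 to 1) | ANOVA power |
|---|---|---|
| 0% | 1.50 | 79% |
| 1% | 1.61–1.65 | 72–70% |
| 2% | 1.71–1.78 | 66–62% |
| 5% | 1.96–2.11 | 50–44% |

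Example, p = 2% and μ = 1: 0.98 × 2.25 + 0.0196 × 49 = 3.165, so SD = 1.78 and f = 0.294/1.78 = 0.165. If SD 1.5 already includes deaths, nothing is lost against the plan.

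**3. ANOVA against an ordinal test near the plan's inputs.** Simulation with 80 per arm, 20,000 trials per scenario, both doses equally effective, and baseline held constant. The Kruskal-Wallis test stands in for the proportional-odds score test. The protocol gives no category distribution and no expected death rate for the trial, so day-28 survivor means of 1.2 to 2.2 and deaths of 0 to 5% are assumptions.

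| Scenario | Ordinal minus ANOVA (percentage points) |
|---|---|
| A1. Total SD about 1.5, f about 0.20, proportional odds over the whole scale, deaths 0–3% | +2 to +11 |
| A2. Same SD and f, deaths equal in all arms at 0.5–3% | +4 to +21 |
| B. f = 0.20 in survivors, equal deaths added: 0% / 2% / 5% | +1 to +8 / +13 to +25 / +23 to +38 |
| C. Effect only on scores 5–8 (75% reduction, illustrative) | −34 to −42 |

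In A1 with no deaths, a survivor mean of 1.2 gives 77.0% for ANOVA and 88.0% for the ordinal test; a survivor mean of 2.2 gives 76.8% and 78.6%. In C, one case with f = 0.20 gives 76.2% and 34.0%.

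**4. A more skewed distribution, with baseline included.** Assumed placebo distribution over scores 0 to 8: 35/40/12/4/3/1/1/1/3 percent. Baseline is 3 (70%) or 4 (30%), drawn independently of outcome, and the common odds ratio is 2.2. The control SD is about 1.75 and f about 0.16, so this case does not match the plan's inputs. Repeated runs agree to within about 3 points.

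| Deaths | ANOVA of change | Rank test of day-28 score |
|---|---|---|
| 0% | 60% | 78–81% |
| 3% | 56–58% | 78–80% |
| 10% | 60% | 80% |

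The gap is about 20 points at every death rate. On the same variable it is smaller: about 6 to 9 points when both tests use change, and about 12 to 19 when both use the day-28 score. If nobody scores 5 to 8 (assumed 35/40/12/8/5 percent over 0 to 4), ANOVA and rank test of change are level at 65% and 66%, yet ANOVA of change still trails the rank test of the score by 14 points. So part of the loss comes from subtracting baseline, and most of the rest from general skew.

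**5. Validity.** Null rejection was 4.2% to 5.2% for all tests.

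**The case against.** The plan's test holds its type I error, and its power calculation matches the test and reproduces. Nothing is invalid; what is at issue is interpretability and efficiency. That stands.

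A reader might infer that a few deaths scored 8 inflate the variance and so cost this trial some 15 to 25 points of power. The documents do not support that. In the skewed example the gap is about the same with no deaths as with 10%. Comparing ANOVA of change with a rank test of the score also mixes two differences: mean versus rank, and change versus score. The odds ratio, the category distribution and the independence of baseline and outcome are all assumed. Nor is it settled that deaths enter at 8: section 11.3(f) removes treatment failures from the primary analyses, and section 17, Missing Data, carries the last observation forward after withdrawal for an adverse event.

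The strongest counterargument is that the direction can reverse. Section 12.1 names prevention of deterioration as a possible action of the drug. If benefit were confined to scores 5 to 8, the mean would be the more sensitive summary by a wide margin. That also stands, and it is why the loss can only be stated conditionally.

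**Conclusion.** The concern holds in conditional form. The primary analysis treats ordered states as equally spaced, so its estimate depends on arbitrary spacing. Against a general shift toward better states its power is usually lower than that of an ordinal analysis of the day-28 score. Under proportional odds the loss is about 2 to 11 points near the plan's f and SD, and about 20 points under one assumed skewed distribution. The larger figure arises partly from change scores and does not need deaths. The advantage turns to ANOVA if the effect is confined to severe outcomes. No single figure is a property of the plan. With 79.3% power at the planned size, even a small loss falls below the stated target. The change is advisable; it does not correct a validity error.

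**What to change.** In section 17:

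- Make the primary analysis a proportional-odds (cumulative logit) regression of the day-28 WHO score, with baseline WHO score and center as covariates. Center is the stratification factor given under Randomization; the closing paragraph of section 17 names other factors, and the two should be reconciled.
- Restate the null hypothesis and the success rule as the two-degree-of-freedom test of treatment in that model. Report the common odds ratio with 95% CI for each dose versus placebo.
- Keep ANOVA of mean change as a sensitivity analysis.
- Say that the ANOVA-based sample size is an approximation for this test, and whether SD 1.5 includes deaths. Align the synopsis.
- Reconcile section 11.3 with the Missing Data text so that deaths and treatment failures enter the primary analysis at their observed score.

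The cost is protocol and analysis-plan text, with no new visits or measurements. Whether 240 patients remain enough under the ordinal test cannot be confirmed without an expected category distribution, which the sponsor would have to supply. The proportional-odds assumption must be checked, and power would be lower than with ANOVA if the drug affects only severe outcomes, so the sponsor should state the pattern of effect it expects.

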10. STUDY DESIGN AND PROCEDURES

240 adult patients who suffer from COVID-19 infection and do not participate in any other clinical trial. Patient must not agree to participate in any new clinical study during the study duration. Study will take place during patient's hospitalization due to COVID-19 infection. The study will last up to 4 weeks, until conclusion on day 28. In case of hospital discharge within the study period, follow up will continue per protocol until day 28 wherever the subject will be located, depending on the status of the patient and study schedule.

If patient discharged, visits will be performed via phone call, if he still hospitalized, visits will be performed at corona department.

Only on day 28, all the patients must undergo clinic visit, they will arrive to the research clinic (only patient who will be under quarantine will have a phone call visit).

The study is not designed to include participants from a special population, so that patients with mental and intellectual problems, lack of judgment, children under the age of 18 and pregnant women will not be allowed to participate, or any patient who have a legal guardian.

Standard of care treatment acceptable to be used while patient participates in study:

Treatment will include:

Supportive care - symptomatic

Painkillers

Anticoagulant therapy

	MGC Pharma Clinical Study Protocol	Protocol No.: MGC-009
		Version 02, 05 Sep 2021
		Page 36 of 76
A Phase IIb, double blind, placebo-controlled clinical study designed to evaluate the effect of CimetrA in patients diagnosed with COVID-19		CONFIDENTIAL

Steroids

REMDESIVIR - Compassionate treatment

Antibiotic treatment as needed

Inhalations if necessary

Oxygen

The treatments offered above are given according to the guidelines of the Ministry of Health.

The treatment will be given to the patient according to the clinical judgment of the medical staff and in accordance with the patient's health condition, and therefore the treatment does not have to be the same in each of the medical centers participating in the study.

10.1. **Enrollment**

Each candidate subject will be reviewed for an inclusion/exclusion criteria. After signing the ICF, the candidate subject will be asked to provide a medical history and undergo a physical examination, including measurement of blood pressure, pulse, temperature (PO), body weight and height, saturation, respiratory rate, vas scale, news score.

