Sample size and Power were calculated with the Power and Precision statistic program ver 4.1 and all statistical analyses and data presentations, including tabulations and listings, will be performed using the SPSS statistic program version 27.0 (or higher) software.

Randomization

Randomization tend to produce study groups comparable with respect to known and unknown risk factors, removed investigator bias in the allocation of participants and guarantees that statistical tests will have valid false positive error rates.

After a participant will meet the eligibility criteria, he/she will be randomly allocated (with a 1:1:1 ratio) to one of the following treatment groups based on a randomization scheme stratified by center.

The randomization scheme will be prepared by an independent statistician using statistic program for random number generator. The block size is set in ahead and study personnel will be blinded to the randomization block size.

Blinding

This is a double-blind study: neither the participants nor the investigators will be aware of arm allocation of each study participant.

Blindness is important to avoid bias. Monitoring and reporting of the success of blindness are important for the reader's confidence of the trial results. Groups should be marked by capital letter and blindness should maintain throughout the study.

Missing Data

Safety data should be collected from non-adherent/withdrawal participants to avoid possible bias.

	MGC Pharma Clinical Study Protocol	Protocol No.: MGC-009
		Version 02, 05 Sep 2021
		Page 62 of 76
A Phase IIb, double blind, placebo-controlled clinical study designed to evaluate the effect of Cimetra in patients diagnosed with COVID-19		CONFIDENTIAL

Prior to analyzing the data, extreme laboratory values should be checked. Missing values will be treated as ITT.

Multiple imputation for binary data will be used as the primary imputation method in the case of missing data for the primary efficacy endpoint.

Dropout/AE Imputation: A participant with no post baseline measurement or a participant withdrawn due to an adverse event or treatment intolerability will use last observation carried forward imputation methods.

Baseline Data

Baseline participant characteristics will be collected at screening. The specific baseline (“start of treatment”) endpoints and other symptoms will be collected prior to each treatment.

Significance Levels and Handling of Type I Error

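### The primary model names neither centre, the stratification factor, nor the day 1 WHO score; the cost is some power and over-wide intervals, not false positives

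*Protocol*

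**What the plan says.** All of this is in the Protocol, mostly in section 17.

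- **Randomization:** patients are allocated 1:1:1 "based on a randomization scheme stratified by center".
- **Primary Efficacy Analysis:** the endpoint is mean change in the WHO Ordinal Scale, and "It will be evaluated using a General Linear Model ANOVA test". No model terms are listed.
- **Planned Sample Size:** "We expect medium effect ($f=0.20$) for the differences in Delta between the 3 groups, and standard deviation of 1.5". The calculation is for a one-way fixed-effects ANOVA with three levels, 80 per group.
- **Subset Analyses:** "The primary endpoint will also be evaluated stratified by center using a General Linear Model ANOVA test". For the rest, "Adjustment for other covariates such as demographics or other baseline participant characteristics may be performed by adding these variables into a multivariate linear regression".
- **Significance Levels and Handling of Type I Error:** "The overall significance level for this study is 5% using two-tailed tests", except that a treatment by centre/region interaction is tested at 10%.
- **Section 9.1 and Table 5:** the WHO score is recorded on day 1. Patients must be hospitalised and scores of 5 or more are excluded (sections 11.1 and 11.2), so baseline can only be 3 or 4.
- **Section 10, repeated in 13.2:** on standard of care, "the treatment does not have to be the same in each of the medical centers participating in the study".
- **Randomization and stratification (end of section 17):** this describes something else, namely allocation in sets of four across four groups and stratification by medical history and risk factors.

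**The concern.** When allocation is balanced within centres, variation between centres cancels from the arm comparison. A one-way ANOVA nevertheless leaves that variation in the residual, so its standard error is larger than the design warrants. Intervals are then too wide, the test runs below its nominal level, and power is forgone. The protocol gives reason to expect centre differences: four countries, and care that may differ by site.

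The day 1 score enters only by subtraction. That is full adjustment only if the final score moves one for one with baseline. Otherwise some explainable variance stays in the residual.

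The planned sample size has little slack, so efficiency available at no cost is worth taking.

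**Working it through.** **Inputs from section 17:** N = 240 in three arms, f = 0.20, SD of change 1.5 (variance 2.25), two-sided alpha 0.05, target power of at least 80%. **Not given in the protocol, so assumed:** the variance share due to centre, the number of centres, the share of patients starting at score 4, and the slope of the final score on baseline.

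**1. The plan's own figure.** One-way ANOVA, non-central F with 2 and 237 degrees of freedom and λ = N·f² = 240 × 0.04 = 9.6. Power is 79.3%. Reaching 80% takes 246 patients (82 per arm). The stated 240 reproduces to within rounding, marginally under target.

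**2. Power with adjustment.** If centre and baseline together explain a share R² of the variance of the change, λ becomes 9.6/(1 − R²) and the standard error shrinks by √(1 − R²).

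| R² (assumed) | λ | SE factor | Power, no df removed | Power, 12 df removed |
|---|---|---|---|---|
| 0 | 9.60 | 1.000 | 79.3% | 79.3% |
| 0.02 | 9.80 | 0.990 | 80.2% | 80.1% |
| 0.05 | 10.11 | 0.975 | 81.5% | 81.4% |
| 0.10 | 10.67 | 0.949 | 83.6% | 83.6% |
| 0.15 | 11.29 | 0.922 | 85.8% | 85.7% |
| 0.20 | 12.00 | 0.894 | 87.9% | 87.9% |

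Twelve extra degrees of freedom cost about 0.03 points, so adjusting loses almost nothing even if centre and baseline explain nothing.

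**3. What baseline alone can contribute.** Let p be the share starting at 4 and b the slope of the final score on baseline. The change then has slope b − 1 on baseline, so R² = (1 − b)²·p(1 − p)/2.25.

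- p = 0.5, b = 0: 0.25/2.25 = 11.1%, the maximum for slopes 0 to 1 (power 84.1%).
- p = 0.5, b = 0.5: 0.0625/2.25 = 2.8%.
- p = 0.25, b = 0.5: 0.0469/2.25 = 2.1%.
- p = 0.10, b = 0: 0.09/2.25 = 4.0% (power 81.0%).
- p = 0.05, b = 0.5: 0.0119/2.25 = 0.5% (power 79.5%).
- b = 1, any p: 0%.

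Section 11.1 asks for oxygen saturation of at least 94% on room air. That makes a small p plausible, so baseline may add little.

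**4. Calibration when centre is ignored.** Centre-stratified block randomisation was simulated with 4 or 12 centres and blocks of 6 (all assumed), using 3,000 null runs and 2,000 power runs per setting. Monte Carlo error is about 0.4 points for type I error and 0.9 for power.

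| Centre share of variance | Type I error, unadjusted | Type I error, centre in model | Power, unadjusted | Power, centre + baseline |
|---|---|---|---|---|
| 0 | about 5% | about 5% | about 79–80% | 79–84% |
| 10% | 3.5–4.3% | about 5% | 80–81% | 84–89% |
| 20% | 2.7–3.5% | about 5% | 80–83% | 88–92% |

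The unadjusted test does not fall below its planned power. The loss is relative to the adjusted analysis that the same data would support.

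**The case against.** **The text does not say that the primary model is unadjusted.** A general linear model can hold centre and baseline, and model terms are often left to the SAP. This is fair as to wording. But the one-way power model, the absence of any named term, and the placing of the centre-stratified analysis as an addition under Subset Analyses all point the same way. The protocol has assigned these terms to other analyses; it has not simply left them open.

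**Centre is not neglected.** A centre-stratified analysis is a commitment, and an interaction test that needs centre in the model is planned. This stands: the issue is which analysis is primary. Likewise, the optional-adjustment sentence concerns other covariates in supplementary analyses, so it does not make the choice of primary test optional.

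**Baseline may not help.** A reader might infer that because oxygen use at entry is strongly prognostic, adjusting for it must gain a lot. The formula shows the opposite for a change score: the nearer the slope is to 1, the more subtraction has already done, and at slope 1 the gain is nil. This stands, and it is why centre carries the argument.

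**Large gains need a corner case.** The 87.9% figure needs 20% of variance explained, for example half the patients at score 4, slope 0 and a centre share near 10%, with no overlap between the two. The protocol supports none of these values.

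**Conclusion.** The point holds as a modest, nearly cost-free gain in efficiency and calibration. The planned primary model, on its most natural reading, omits the factor on which randomisation is stratified and uses the day 1 score only by subtraction. If centre and baseline explain 2% to 10% of the variance, which is an assumption, adjustment lifts power from 79.3% to between 80.2% and 83.6%. Baseline alone contributes 0% to 11% of variance for slopes from 0 to 1, and probably little if few patients start at score 4.

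A reader might infer that the unadjusted ANOVA endangers the trial's validity. The design does not support that. Ignoring centre after stratifying by it keeps type I error at or below 5%. That a patient starting at 4 has more room to improve than one starting at 3 creates no bias between randomised arms. If the centres do not differ, the calibration concern vanishes too.

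**What to change.** 1. First reconcile the two stratification statements in section 17 (by centre under Randomization; by medical history and risk factors, with sets of four for four groups, in the later paragraph). The model should carry the factors actually used.
2. State that the primary analysis is a linear model of the WHO score at Day 28, or of its change to Day 28, with arm, centre and baseline WHO score (3 or 4) as prespecified terms. With baseline in the model, both outcomes give the same arm contrasts.
3. Pool small centres within country by a rule fixed before unblinding.
4. Keep the unadjusted ANOVA as a sensitivity analysis, and remove the optional wording for these terms under Subset Analyses.

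No new data, visits or patients are needed. The cost is the reconciliation of the stratification text, the pooling rule and a negligible loss of degrees of freedom.
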